3.6 DATA SOURCES

3.6.A QUESTIONNAIRES

Questionnaires will be administered at baseline, 1-, and 6-month study visits to collect information about participant demographics (e.g., age, gender), stigma scores, sex risks, substance use risk behaviors, care utilization, general and mental health.

3.6.B SESSION AUDIO RECORDINGS

We will audio-record all intervention sessions and will code a subset of these recordings for quality assurance and fidelity monitoring, i.e., to document adherence to the intervention study procedures.

3.6.C INTERVENTIONIST ADHERENCE CHECKLIST

Interventionists will fill out an intervention adherence checklist to document the items of the intervention that were covered (i.e. specific metaphors, emphasis on homework, etc.)

4. STUDY PROCEDURES

4.1 RECRUITMENT

Participants enrolled in the Stigma, Risk Behaviors and Health Care among HIV-positive Russian People Who Inject Drugs (SCRIPT) study will be recruited by staff from a civil society organization (CSO) in St. Petersburg, Russia.

4.2 PHONE SCREENING

Participants who express interest in joining the study at the CSO, will be given the opportunity to participate in a phone screening. The CSO staff will call the rehabilitation center and notify the SCRIPT RA that a CSO client is potentially interested in the study and would like to complete a phone screening. The rehabilitation center RA will conduct a Brief Screening Agreement specific to the phone screening. If deemed eligible from the phone screening, the staff at the CSO will provide clear instructions to using the public transportation system to get to the rehabilitation center. The instructions will have contact information for the rehabilitation center if any issues arise. The potential participant may also receive help from the CSO outreach worker for transportation (i.e. metro card, taxi).

If a participant is acutely sick and/or still in withdrawal when approached for phone screening, the CSO staff will re-approach that person later (if the person is interested) when this person presents again at the CSO.

4.3 SCREENING

In-person screening for the SCRIPT study will take place at a rehabilitation center by rehabilitation staff. Rehabilitation staff will be appropriately certified in human subjects research and trained as research assessors (RA) to do the screening procedures. They will be on the local protocol as staff under the Pavlov IRB.

A RA will conduct screening, and will meet with the potential participant in a private room to briefly describe the study and conduct in-person screening to confirm the presence of inclusion criteria and the absence of exclusion criteria.

If a potential participant arrives at the rehabilitation center for in-person screening acutely sick and/or still in withdrawal, the RA will invite the individual to come back later (if the person is interested) when this person presents again at the rehabilitation center (i.e., once the person is eligible for screening and/or eligible for the study, they can be enrolled once they are feeling better).

The rehabilitation center will keep a list of names phone-screened to prevent re-screening. This list will contain no other information other than names, contact information (if eligible), and eligibility status and will not be linked to screening data. This list only serves to avoid repeat screening. We will ask CSO staff and RAs to not refer potential participants again who previously did not screen into the study. However, we will not link participants' reasons for ineligibility to their names (or any other identifiable information). Informed consent will take place immediately after screening and if, for some reason it cannot, the data from the screening will not be retained. Answers to phone screening questions will be recorded in a different REDCap project than the basic personal information (name and contact information). Participants who were phone screened as eligible, will be asked to come in for an in-person screening which will serve as the documentation data.

Protocol for ensuring double randomization and double enrollment do not occur

1. Prior to screening, the RA verifies that the participant was not previously referred for screening.
2. The RA searches the name of the participant in the SCRIPT tracking system in REDCap to confirm that the patient has not been previously enrolled in the SCRIPT Study. If a match appears, the RA checks DOB and address. (This will be done confidentially, so that the patient does not know that there is someone with the same last name already in the study, to protect the confidentiality of the enrolled participant.) If no match is found, the RA proceeds with screening.

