1. INTRODUCTION

1.1 SUMMARY

People who use drugs (PWID) often experience multiple layers of stigma when they are living with HIV.¹ Stigma is defined as the social exclusion and dehumanization of individuals in an undesirable social category.² Interventions to help affected PWID living with HIV cope with the dual stigma related to HIV and substance use have not been studied specifically in this population. Among people living with HIV, stigma adversely impacts all aspects of the care cascade: timely HIV testing, diagnosis, treatment, adherence and retention in care.³⁻⁵ Among PWID, drug use may add to adverse social factors and create particular stigma vulnerability. Russia is a country where PWID and other HIV key populations are highly stigmatized and face discrimination. Furthermore, agonist treatment for opioid use disorder is illegal in the Russian Federation. People with substance use disorders and those living with HIV have to register with the local authorities for treatment. While many try to avoid registration, most PWID and people living with HIV (PLWH) are known to the authorities. Further qualitative findings suggest that in the absence of public anti-stigma campaigns in Russia, stigma reduction interventions should address internalized stigma and their determinants to help affected people cope with the dual stigma. Stigma interventions should be adapted to address not only affected people's shame and guilt, but also their felt hopelessness. These emotions and related feelings such as avoidance and fear of being rejected may negatively affect people's agency and mental health.^{7,8} We are proposing *Acceptance and Commitment Therapy* (ACT) as a potential behavioral intervention to target the emotions underlying internalized stigma and thus empower affected people. ACT has been shown to increase engagement in addiction care.⁹ Its use and efficacy to reduce stigma has not yet been explored among HIV-positive PWID.¹⁰ The objective of this study, "Stigma, Risk Behaviors and Health Care among HIV-positive Russian People Who Inject Drugs (SCRIPT)," is to implement and evaluate the feasibility of an adapted form of ACT targeted to PWID living with HIV in Russia as an intervention to reduce intersectional HIV and substance use stigma via a two-armed randomized controlled trial among 100 HIV-positive PWID. The central hypothesis is that ACT is feasible and can be delivered to decrease HIV and substance use stigma scores.

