2.7 INCLUSION CRITERIA

To be eligible to participate in the trial, participants will need to meet the following inclusion criteria:

1. 18 years old or older
2. HIV-positive
3. Current injection drug use (past 30 days)
4. Not currently on ART
5. Provision of contact information for two contacts to assist with follow-up
6. Address within 100 kilometers of St. Petersburg
7. Not enrolled in any other research studies
8. Possession of a telephone (home or cell)
9. Able and willing to comply with all study protocols and procedures over 6 months
10. Available at the specific days of the week and times that the group sessions will be occurring for the subsequent 3-4 weeks (to ensure that participants randomized into the intervention arm will be able to receive the intervention)

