6. PARTICIPANT SAFETY

Boston Medical Center, First St. Petersburg Pavlov State Medical University/Global Health Institute and their Institutional Review Boards (IRB), the Principal Investigator ([name]) and the site PI and project manager are responsible for monitoring the pilot RCT proposed for the R00 phase and for ensuring the safety of participants. As the research is conducted in Russia, [name] will verify at each weekly conference call meeting if any adverse events or unanticipated problems occurred. The Russian investigators will notify the PI by email of serious incidents the same day. Discussion will take place on whether or not the incident meets the definition of an Unanticipated Problem (UP): is unexpected, possibly related to being in the research, and places subjects or others at greater risk of harm. Discussion will also take include if protocols or consents need to be modified, and if/when the incident should be reported to the IRBs. The principal risk of the study is breach of confidentiality. The remaining risks are minimal.

Participation in this study presents “minimal risk” which is defined as “the probability and magnitude of harm or discomfort anticipated in the research are not greater in and of themselves from those ordinarily encountered in daily life or during the performance of routine physical or psychological examinations or tests,” (from 45 CFR 46.102(i)). The primary risk of the study is the risk of loss of confidentiality. This risk and

any other risk of study participation are addressed above and within Protection of Human Subjects. The risk of breach of confidentiality is best addressed by appropriate study procedures; however, the PI will be responsible for assuring that study procedures are adhered to regarding data security, data transfer, and communications in tracking participants by meeting regularly with study staff, reviewing procedures, and performing quality control reviews of study forms as described above.

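### An eligible entry on the named phone-screening list itself reveals HIV status and injection drug use, and no rule removes it for callers who never enrol

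*Combined protocol and SAP*

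**What the plan says.** Section 4.3 states the list's existence and purpose: "The rehabilitation center will keep a list of names phone-screened to prevent re-screening". Its contents are given as "names, contact information (if eligible), and eligibility status and will not be linked to screening data". Phone-screen answers go into a separate REDCap project from name and contact details, and the reasons why someone failed screening are not tied to that person's name. On retention, the section expects consent to follow screening directly and says that "if, for some reason it cannot, the data from the screening will not be retained".

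Section 2.7 defines eligibility: "To be eligible to participate in the trial, participants will need to meet the following inclusion criteria". HIV-positive status is criterion 2. Criterion 3 begins "Current injection drug use (past 30 days", and criterion 4 is "Not currently on ART".

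Section 4.2 has the research assessor at the rehabilitation center conduct a Brief Screening Agreement for the phone screen. Written informed consent comes later, in person (section 4.4).

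Section 6 ranks the risks: "The principal risk of the study is breach of confidentiality".

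**The concern.** The evident aim of section 4.3 is that no name should sit beside a sensitive screening answer. That works for people who fail the screen, because ineligibility does not show which criterion was missed. It works less well for those who pass, because passing means that every criterion assessed was judged met. The more sensitive group has the weaker protection.

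Retention adds to this. The rule that discards screening data when consent does not follow says nothing about the list, and a list meant to prevent repeat screening has to be kept. Someone who passes the phone screen and never attends, or attends and declines, therefore stays recorded by name, status and contact details.

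At stake is the risk that the protocol itself puts first. Section 1.1 gives the setting: "While many try to avoid registration, most PWID and people living with HIV (PLWH) are known to the authorities". If the list were lost, copied or demanded, it would point to people as living with HIV and injecting drugs, some of whom never joined the trial.

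**Working it through.** The documents state no figure to reproduce, and the main check is one of logic.

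**Step 1: what the list holds.** Section 4.3 gives name, eligibility status and, for eligible callers only, contact information. Either of the last two fields identifies an eligible caller: the status directly, the contact details because nobody else has them.

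**Step 2: what eligible implies.** The criteria in section 2.7 set against the phone-screener column in section 3.5:

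| Fact | Section 2.7 | Phone screener, section 3.5 | Strength of inference |
|---|---|---|---|
| HIV-positive | criterion 2 | itemised | direct, provisional |
| Injects drugs | criterion 3 (past 30 days) | history of injection itemised; recency not | direct for injection; recency from section 2.7 |
| Not on ART | criterion 4 | not itemised; only a general line for screening questions | by inference from section 2.7 |

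All entries are provisional, because section 4.3 has the in-person screen confirm the criteria. No link to item-level answers is needed to read any row.

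**Step 3: what happens without consent.** The sequence is Brief Screening Agreement, phone screen, list entry, in-person screen, written consent. The non-retention rule covers screening data. No section applies it to the list or gives a deletion date for it. By contrast, audio recordings have a stated deletion time (sections 3.3.A and 7.1).

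**Step 4: whether the purpose needs the status field.** Section 4.3 says the list serves only to avoid repeat screening, and the first step of its duplicate check asks only whether the person was referred before. An already-phone-screened mark answers that. People expected back (awaiting the in-person screen, unwell on arrival, or still deciding under section 4.4) can be found as pending in the tracking system. People unwell when first approached for the phone screen (section 4.2) are re-approached later and need no entry until they are screened.

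**Step 5: how many people.** Let E be the number who phone-screen eligible. With the 100 planned participants in section 2.9 enrolled, eligible non-enrollees = E − 100. The documents do not give E. Purely as an assumption, E from 100 to 200 gives 100 − 100 = 0 to 200 − 100 = 100 people.

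**The case against.** A good case can be made for leaving the text alone.

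- **Callers agree to something first.** A reader might infer that people are listed without any consent. The documents do not support that: a Brief Screening Agreement precedes the phone screen. Its text is not in the protocol and SAP, so whether it covers keeping name and status cannot be judged. What stands is that these callers have not given written study consent.
- **The non-linkage statement is true.** A reader might infer a contradiction, or a safeguard that fails outright. Neither follows. Item-level answers are held apart. The weakness is in what the status field conveys on its own.
- **Eligibility at this stage is provisional.** It would be too strong to say that each entry discloses three facts with certainty. It rests on a phone screen, ART is not itemised there, and the criteria are confirmed only in person.
- **Other controls exist.** Section 7.3 restricts identifiable documents to certain roles and describes user privileges and an audit trail; section 7.1 requires encryption. These lower the chance of disclosure but do not change what the list says if disclosed. The access rule speaks of participant data, so its reach to people who never enrol is unclear.
- **Most of this population is already known to the authorities,** by the same sentence in section 1.1. That lowers the added harm for many, but not for those who have avoided registration.
- **Staff need status to run the workflow.** Section 4.3 asks that people who failed screening not be referred again, while others are meant to return. This stands to the extent that pending callers must be recorded somewhere, and that record will disclose eligibility while it exists. It does not justify a lasting status field.

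**Conclusion.** The point holds as a data-minimisation gap measured against the protocol's own principal risk. For eligible callers, the named list conveys provisional HIV-positive status and injection drug use, with absence of ART as an inference, and nothing in the plan removes the entry when written consent does not follow.

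The group concerned is eligible non-enrollees. It is tempting to count the 100 planned participants as exposed too, but consent forms and the tracking system already identify them as trial members, so the list adds little for them. The number of non-enrollees is not given, and the 0 to 100 above is only an illustration.

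The conclusion assumes that phone eligibility is judged against the section 2.7 criteria, and that no deletion rule stands in a document not available here, such as the Brief Screening Agreement. It affects no randomisation, estimate, error rate or sample size. The change is worth making because it is cheap.

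**What to change.** In section 4.3:

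1. Limit the lasting repeat-screening list to name, or preferably a one-way code made from it, and an already-phone-screened mark. Leave out eligibility status and contact details, and do not add date of birth in clear.
2. Hold contact details of callers who await in-person screening or are still deciding in the access-restricted tracking project.
3. Delete those details when the person declines, is found ineligible at the in-person screen, or has not enrolled by a stated time, and at the latest when recruitment closes. Square the stated time with section 4.4, which sets no limit on how long someone may consider participation.
4. Say that the access limits in section 7.3 also cover people screened but not enrolled.

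The cost is protocol wording and a change of fields. Staff must open the tracking project to see who is pending. Once a pending record is deleted, a returning caller can no longer be told apart from someone who failed the screen. Some disclosure remains while a caller is pending, and a name on the lasting list still shows contact with the study. The change reduces the exposure but does not abolish it.

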4.4 INFORMED CONSENT

An RA will conduct the consent process as well as obtain written consent. After eligibility and interest in enrollment is determined, an RA will administer and document the informed consent of the participant in a private location, such as a private room at the study site or at a location of the potential participant's preference. If participants are unsure whether they would like to participate, they will be allowed any amount of time they wish to consider participation in the study. If the participant is not able to make a decision on the day of the initial visit, s/he will be invited to contact the study team once s/he have made their decision. The

study will be explained to eligible participants who will be offered participation in the study. Research assessors will answer any questions the patients may have including risks, benefits and alternatives (including non-participation) to participation, and will provide written materials describing the study. The written informed consent (in Russian), including the risks, benefits and alternatives, will be signed and dated by the participant and the research assessors. A signed copy of the informed consent will be provided to the participant, and a copy will be maintained by the research team. Potential participants will be informed that refusal to participate will not affect their medical care in any way and they will be informed of their right to drop out of the study at any time.

4.5 VISIT FLOW

We aim to screen and consent eligible participants, followed by baseline assessment (about 60 minute duration) on the same day. The first ACT group session (about 120 minute duration) will occur once five participants have been randomized into the intervention group and are all available for the pre-scheduled group session. After eligible participants are consented and enrolled, the following will take place at the **Baseline visit**:

- Collection of locator/contact information and verification of contact phone numbers
- Administration of assessment questionnaire
- Randomization
- Compensation and scheduling next visit

Intervention Group:

- Participants randomized into the intervention group will have their group ACT sessions consecutively on weeks 1, 2, and 3.

Intervention and Control Group:

- During the **1-, and 6-month in-person assessments**, the Research Assessor will:
 - Review and update locator/contact information, verifying new numbers, as necessary
 - Administer assessment questionnaire
 - Compensate participant and schedule next visit (1-month visit only)

4.6 QUALITY ASSURANCE

Informed consent quality assurance

The Research Assessor will review Informed Consent Forms (ICFs) for completeness with the participant present. Items to check will include, but are not limited to: responses/initials collected for all questions, correct version of ICF used, signed and dated by both participant and Research Assessor. The Local Study Coordinator, who will oversee all RAs, will review all completed consent forms weekly and will complete the Consent Form Deviation log if any errors are identified.

Assessment quality assurance

During the assessment, if the participant provides conflicting answers or answers that did not make logical sense (either within the same section or between sections), the Research Assessor will gently try to help the participant arrive at more logical answers. However, the Research Assessor will not force the participant to change his or her answers. Certain quality assurance checks are built into the assessment. The system will flag any inappropriate responses and prevent the Research Assessor from continuing until the issue is resolved. If many “refused” options are selected, the RA will offer the participant the opportunity to complete those sections (the Research Assessor will accept the participant’s refusal if he or she does not wish to complete the section). The Research Assessor will never guess to correct a mistake. The only instance when a change can be made to the completed assessment is in the event that the Research Assessor is 100% certain that an error was made in data entry. Local data manager will QC all paper forms used for the assessment (i.e., rulers for VAS). Upon completion of QC of paper forms, the reviewer will write their initials and date of review at the bottom of the forms.

ACT intervention quality assurance

The ACT stigma intervention will be delivered by clinical psychologists. Supervision will be provided by site PI and an ACT trainer. Interventionists and supervisors will be trained by ACT trainers. To assess interventionist fidelity to ACT, we will use an ACT Fidelity Measure to rate the recorded intervention videos/tapes, with a focus on interventionist behavior and competency. The measure classifies three different targets of clinician behaviors, openness, awareness, engagement, as well as interventionist stance. This will also allow us to investigate how combinations of interventionist behaviors relate to outcomes and help train future interventionists in Russia and Russian speaking countries.

3.6.B MISSED VISITS

The following procedures will take place in the event of an intervention participant missing their group session. If they miss their:

1st session: We will schedule them into the next available group.

2nd session: We will ask them if they would like to participate in an individual make-up session. This will be an adapted session conducted by one of the interventionists who is trained specifically in this individual session. If they choose to not participate in the make-up session, they will still be scheduled for their 3rd session and for their 1-month and 6-month assessments.

3rd session: This will be a missed session, but they will still be invited for their 1-month and 6-month assessments.

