3. INTERVENTION

3.1 INTERVENTION OVERVIEW

The study will randomize 100 PWID living with HIV in the St. Petersburg area. We will approach potential participants at CSOs serving PWID and people living with HIV (PLWH). After a phone-screening, potential participants will be given clear transportation instructions to the location of the remainder of the procedures (in-person screening, consent, enrollment, assessments, intervention sessions). After in-person screening, consent, enrollment, and the baseline assessment, participants will be randomly assigned to either the SCRIPT intervention or standard of care. Following randomization, participants in both groups will receive standard of care at the study site.

Following randomization by RAs at the rehabilitation center, participants in the intervention group will be scheduled to engage in group ACT sessions. These will consist of three 2-hour group sessions of culturally adapted ACT to reduce stigma and related manifestations in weeks 1, 2 and 3. The ACT sessions are described in further detail in 3.3.A.

Throughout the course of the study, participants will be expected to participate in three in-person assessments (baseline, 1 month [4 weeks], and 6 months [24 weeks]). Participants in the intervention groups will receive three ACT sessions over one month in approximately 13 groups of 5 people each (n=65), with a final assessment conducted at 6 months.

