5. ASSESSMENTS

5.1 BASELINE ASSESSMENT

The baseline assessment will be conducted immediately following the screening and informed consent. The assessment will be interviewer-administered.

Participants will be assessed as part of this study using validated interview instruments covering the following topics, which will take approximately 60 min:

- Demographics, modified from the ASI Lite-CF Clinical/Training Version and Addiction Severity Index⁷
- ART Medication Use and Adherence
- HIV Sex Risk Behaviors, questions are adapted from the Women's Health Coop Baseline Questionnaire
- HIV Risk Categories, using questions adapted from the American Red Cross and Navaline et al.¹⁷
- HIV Disclosure, using questions from Stein et al. (1998)¹⁸ and Raj et al. (2006)¹⁹
- HIV Stigma, using the Berger et al. HIV stigma scale²⁰ and Leickness et al.
- Substance Use Stigma^{21, 22}, via a modified Substance Abuse Self-Stigma Scale
- Substance Use enacted interpersonal stigma, through the Stigma-Related Rejection Scale (SRS)
- Psychological flexibility, by the Acceptance and Action Questionnaire – Substance Abuse (AAQ-SA)
- Mental health through the Patient Health Questionnaire (PHQ-9)
- Anxiety by the GAD-7
- Partner Violence and Sexual Assault, adapted from the TAJ assessment
- Alcohol Use, via the AUDIT-C²⁸
- Perceived alcohol stigma, using questions from Luoma et al. (2010)
- Drug use by an adapted version of the Risk Behavior Survey^{30, 31}
- Overdose and Suicide, using adapted questions from Britton et al. (2012)³⁴
- Social Support, using the harmonized STTR document^{35, 36}
- VR-12 Health Survey & MOS-HIV^{37, 38}
- Care utilization
- Post-Traumatic Stress Disorder via the Abbreviated PTSD Checklist
- Police involvement
- HIV Testing History

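### The consistency prompt in Section 4.6 exempts no scale, so an assessor who can know the arm may influence answers on the primary stigma and satisfaction scales

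*Combined protocol and SAP*

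**What the plan says.** The assessment quality assurance text in Section 4.6 covers answers that conflict or make no logical sense, "either within the same section or between sections". In that case "the Research Assessor will gently try to help the participant arrive at more logical answers". The text does not define what counts as logical and exempts no instrument. It adds that the data system flags inappropriate responses and will "prevent the Research Assessor from continuing until the issue is resolved".

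The same paragraph sets limits:
- On guesswork: "The Research Assessor will never guess to correct a mistake".
- On pressure: "the Research Assessor will not force the participant to change his or her answers".
- On edits once the interview is over: "The only instance when a change can be made to the completed assessment is in the event that the Research Assessor is 100% certain", where the certainty must concern a data-entry error.

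On who conducts the interview, Section 5.1 says of baseline: "The assessment will be interviewer-administered". For 1 and 6 months, Section 4.5 has the RA administer the questionnaire, and Section 9.1 gives all assessments to RAs. Section 3.1 describes the step "Following randomization by RAs at the rehabilitation center".

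Sections 2.1 and 8 name the primary outcomes. For Aim 1 it is satisfaction at 1 month. For Aim 2 they are an HIV internalised shame scale and a modified substance use self-stigma scale, both at 1 month.

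**The concern.** Prompting a participant to reconcile two answers is ordinary data cleaning when a fact lies behind them, such as a date, ART use or a count. Shame and self-stigma items have no such target. A person can hold mixed feelings, and a mixed set of answers may be correct. Section 3.3.A says the intervention does not try to remove shame but teaches participants to notice it and loosen its link to behaviour. Answers that look contradictory are therefore plausible in the ACT arm, and the prompt could fire more often in one arm than the other.

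If the person deciding what is logical can know the arm, a well-meant suggestion can move answers in the expected direction. For the stigma scales this would bias the comparison between arms. For satisfaction it would raise the single-arm score on which the feasibility conclusion rests.

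**Working it through.** The point is mainly textual. The plan gives no SD, effect size or significance level for these outcomes, so there is no figure to reproduce.

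**Step 1. Does the prompt reach the primary scales?** Yes. It applies within and between sections, and neither Section 4.6 nor Section 5 excludes any scale.

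**Step 2. Can the follow-up assessor know the arm?** Yes, by inference from four places:
- RAs, as a role, randomise (3.1) and perform all assessments (9.1).
- The footnote to the Section 5.2 table restricts the satisfaction items to the intervention group, so whoever gives them learns the arm.
- Follow-up windows run from the first group session in the ACT arm and from baseline in the control arm (3.5.A).
- Some interventionists are staff of the rehabilitation center, as the RAs are (2.6).

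No section describes blinded assessment.

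**Step 3. When can prompting depend on the arm?** Only at follow-up. Section 4.5 places the baseline questionnaire before randomisation. The Aim 2 primaries and satisfaction are all measured at 1 month, so they are exposed.

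**Step 4. Do the limits close the route?** No. Not forcing and not guessing rule out coercion and invention. The certainty rule governs a completed assessment. None of the three addresses suggestion while the interview is under way.

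**Step 5. Illustration for a stigma scale.** Inputs: 65 ACT and 35 control (Section 2.4). Assumptions: two-sided 5% test, normal approximation, no true effect, no dropout, no clustering, and an average arm difference of d SD caused by prompting.

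SE = √(1/65 + 1/35) = 0.2097 SD

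False-positive rate = Φ(d/SE − 1.96) + Φ(−d/SE − 1.96)

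| d (SD) | d/SE | False-positive rate |
|---|---|---|
| 0 | 0 | 5.0% |
| 0.1 | 0.477 | 7.6% |
| 0.2 | 0.954 | 15.9% |

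An exact 2:1 split as in Section 3.2, taken as 67:33, gives SE = 0.2127 and 7.6% and 15.6%, so the split hardly matters.

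**Step 6. What would those shifts require?** The prompt fires only on answers judged inconsistent. If a fraction f of participants is prompted on a scale, the net one-directional shift needed in each of them is d/f. Values of f are assumptions.

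| f | d = 0.1 SD | d = 0.2 SD |
|---|---|---|
| 10% | 0.1/0.10 = 1.0 SD | 0.2/0.10 = 2.0 SD |
| 30% | 0.1/0.30 = 0.33 SD | 0.2/0.30 = 0.67 SD |

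With rare prompting, the larger shift needs an implausibly large change per person. With common prompting, it does not.

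**The case against.** The strongest reply is that this is a clarification of wording. The instruction is gentle, the participant keeps the final say, and only answers that look inconsistent are touched. The error rates in Step 5 would be the same for any unblinded-assessor bias and are tied to no observed prompting rate. All of that is right, and it is why the figures serve as illustration only. It does not remove the gap: the rule has no boundary at the attitude scales, and nothing in it prevents suggestion.

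A reader might also infer four stronger things that the documents do not support:
- *That pre-prompt answers are lost.* Section 7.3 describes a REDCap audit trail that logs field modifications, so a saved value that is later changed leaves a record. What escapes is an answer revised aloud before entry, and 4.6 does not ask for that to be noted.
- *That the between-arm comparison of satisfaction is biased.* Section 8.1 mentions two-sample t-tests for satisfaction scores, but by the Section 5.2 footnote there are no control scores. The risk there is an inflated single-arm score.
- *That the same individual randomises and later interviews a participant.* The text assigns both tasks to RAs as a group and says no more.
- *That assessors are told to push answers in a favoured direction.* The text speaks of help with consistency, and no sentence declares the assessors unblinded.

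A further objection concerns the remedy. Recording every scale answer exactly as first given would preserve misheard items and reversed response directions, which are errors. That is fair, and the fix allows for it.

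**Conclusion.** The concern holds. Section 4.6 lets an interviewer who can know the arm prompt for consistency on the scales that are the primary outcomes, and its limits do not exclude suggestion. The consequence is a possible arm-dependent shift on the two stigma scales and a possible upward shift in the ACT-only satisfaction score.

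The documents give no prompting rate and no effect per prompt, so the size is unknown. The rates of 7.6% and 15.9% are conditional on assumed whole-arm shifts of 0.1 and 0.2 SD and ignore clustering; they should not be read as an estimate of harm in this trial. The conclusion rests on the absence of any exemption in 4.6 and on an inference, well supported but nowhere stated outright, that assessors can know the arm. The change is worth making because the route is written into the protocol and is easily closed.

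**What to change.** Amend Section 4.6 as follows:
- Limit the consistency prompt to factual items such as dates, ART use and counts.
- On the stigma, satisfaction and psychological flexibility scales, allow no consistency prompt. The assessor may only re-read the item and its response options verbatim, when the participant has misheard or asks.
- Where an answer changes after a prompt or re-reading, record the first answer and a flag. The audit trail alone would miss a change made before entry.
- State that the suicide safety procedure in Section 6.2, which starts from PHQ-9 item 9, is unaffected.

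The cost is a few sentences, a short addition to assessor training, and a field for the first answer and flag on the electronic form. The downside is that a few inconsistent scale responses stay in the data. The change does not blind the assessors; it removes one route by which knowledge of the arm could reach the answers.
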